Patients who have been scheduled for a PNE procedure will be will be consented for the study on the day of the procedure and screened for participation prior to the procedure by phone. Participants will be randomized with a stratified block randomization scheme (with a random block size of 4, 6, and 8 participants). Randomization sequence will be generated by statistician collaboratorr. All data will be recorded in the RedCap software and be maintained in that password-protected format until analysis. Data analysis will be performed by researchers associated with the IRB for this study. De-identified data will also be sent to statistician collaborator for analysis. The trial is powered to detect a change in VAS pain score of 1.5 points or more on a 10 point scale, a value that is taken to be the minimum clinically meaningful change for the VAS instrument.^{8,9} Data on identification key will be deleted at the conclusion of this study. Patient enrollment will conclude when 34 subjects, 17 of each group, have been enrolled in the study. Sample size was determined using G*Power so that we have 80% power to detect a difference between groups of the minimum clinically meaningful effect size of 1.5 points or greater using the two-sample test at α =0.05 and an assumed standard deviation for VAS score of 1.5 points.

Inclusion criteria:

- 1. Female patients undergoing sacral neuromodulation for the management of their OAB with SMN trial with PNE without fluoroscopy.
- 2. No contraindication to the use of lidocaine patch
- 3. Age >18 years old

Exclusion criteria

- 1. Patients who are not candidates for SNM therapy
- 2. Patients with contraindication to SNM including pregnancy
- 3. Allergy to lidocaine or adhesives
- 4. Chronic pain as an indication for the PNE procedure

Study design

[figure not shown]
The study design will be a double-blind randomized control trial comparing 4% lidocaine patch placed over the sacrum 30 minutes prior to the procedure to placebo patch. Intervention and control patches will be in envelopes labeled with study number and located within the procedure area. A patch from the envelope corresponding to the patient will be placed by a medical assistant or co-investigator who is not associated with the PNE placement procedure 30 minutes prior to the procedure start. Number of voids and incontinence episodes per day

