Page **6** of **17** Version Date: prior to the PNE procedure will be recorded. A patch (intervention or control) will be removed by a medical assistant prior to provider entering the room in order to secure blinding. 1% lidocaine will be injected into the sacral procedure site for adequate pain relief. PNE procedure will then be performed. If inadequate analgesia is reported by the Patient during the procedure, additional injectable lidocaine will be administered, not to exceed 4.5 mg/kg of injectable lidocaine. The volume of injectable lidocaine used will be recorded. VAS pain scores prior to and immediately after procedure will be recorded. Patient Satisfaction Score, rate of successful PNE, rate of progression to SNS implantation, and amplitude of perineal stimulation of a Likert scale will be collected immediately after the procedure.

Patients will follow up in 1 week – as is standard of care with the PNE procedure. Adverse events such as pain or change in sensation will be recorded. Number of voids and incontinence episodes per day after the PNE procedure will be recorded. Overall satisfaction score will be recorded at that time.

In summary, overall questionnaires and data being collected include:

Figure 1: Patient flow and outcomes:

Study has been registered on Clinicaltrials.gov

Participant Recruitment Methods

Subjects will be recruited from the ULP Female Pelvic Medicine and Reconstructive Surgery (FPMRS) practice at the University of Louisville Health Care Outpatient Center (HCOC), Urogynecology Associates office at [name] and the Springs Medical Center. All Patients receiving care at University of Louisville Urogynecology who meet screening criteria will be called prior to their PNE procedure to assess for willingness to participate in this study. Women meeting study criteria will be approached by a member of the research team for consent prior to their PNE procedure. Women interested in the study will have the study explained to them, the consent reviewed, and questions addressed in a confidential manner in a private room. At the time of consent, participants will be informed that their participation in this research is voluntary and that they may discontinue participation without penalty at any time. Participants will not be reimbursed for their participation in this research study.

Informed Consent Process

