- Mild: An experience that is transient and requires no special treatment or intervention. The experience does not generally interfere with usual daily activities.
- Moderate: An experience that is alleviated with simple therapeutic treatments. The experience impacts usual daily activities.
- Severe: An experience that require therapeutic intervention. The experience interrupts
 usual daily activities. If hospitalization (or prolongation of hospitalization) is required for
 treatment of something related to the study drug, it becomes a SAE.

The study uses the follow AE attribution scale:

- Not related: The AE is clearly not related to the study procedure (i.e., another cause of the event is most plausible and/or a clinically plausible temporal sequence is inconsistent with the onset of the event).
- Possibly related: An event that follows a reasonable temporal sequence from the initiation of study procedures, but that could readily have been produced by a number of other factors.
- Related: The AE is clearly related to the study procedures.

Expectedness of Adverse Events:

- Uncommon: discomfort over the area the lidocaine patch was placed and discomfort with the PNE procedure itself
- Rare: Allergy to adhesive bandage or lidocaine, lidocaine toxicity

Plan for Analysis of Results

Summary statistics for demographics, procedures variables, and outcome measures will be summarized for each treatment group (lidocaine patch and control patch) using means, standard deviations, counts and proportions, as appropriate. Differences in these variables will be assessed using the two-sample t-test for continuous variables and the Fisher exact test for categorical variables. A two-sample t-test will be used to assess differences in the primary outcome of change in VAS score after procedure between groups. Differences in secondary outcomes will be considered using the two-sample t-test for continuous variables and the Fisher exact test for categorical variables. Transformations and/or non-parametric methods will be used if continuous data are found to substantially violate the assumption of approximate normality. Multivariate linear/logistic regression models may be used to assess the impact of other variables onto primary or secondary outcomes. Throughout, a significance level of α =0.05 will be used, and all tests will be two-sided. Data analysis will be performed by a biostatistician collaborator using the R statistical software.

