Research Materials, Records, and Privacy

Data that is to be collected with this study and entered into an encrypted database:

Demographic data

- Name
- Date of birth
- Age
- Weight
- BMI
- Race/ethnicity
- Smoking status
- Indication for PNE
- Contact information
- Randomization assignment

Page **13** of **17** Version Date:

- Study ID number
- Number of voids and incontinence episodes per day prior to the PNE procedure and 1

week after the PNE procedure

Procedural variables:

- Total amount of lidocaine used
- Side of PNE lead stimulated
- Amplitude of stimulation at completion of procedure
- VAS pain score prior to and after the PNE procedure.
- Satisfaction scale immediately post procedure and 1 week after the procedure.

1-week follow up variables:

- Adverse events of PNEs such as uncomfortable change in perineal sensation present at the 1 week post-procedure visit
- Patient satisfaction score immediately after the PNE procedure and at the 1 week postprocedure visit
- Number of days with successful stimulation
- Amplitude of stimulation at time of removal
- Bladder/ fecal diary with symptoms during the PNE trial period

3-month follow up

- Number of patients with a "successful" PNE who underwent an implantation
- Number of patients with a "successful" PNE who planned implantation but had not yet scheduled

Page **14** of **17** Version Date:

- Number of patients with a "unsuccessful" PNE who underwent staged procedure
- Number of patients with a "unsuccessful" PNE and what other treatment options they pursued in the next 3 months

Successful PNE is defined as PNE procedure which resulted in successful wire placement.

Unsuccessful PNE is defined as PNE procedure which did not result in successful wire placement.

Implantation defined as stage 2 procedure after interval PNE results showed >/=50% symptom reduction.

Staged procedure is a stage 1 procedure in the operating room as opposed to being performed as an outpatient PNE

This information will be sourced from the subjects themselves and questionnaire templates for satisfaction score and VAS pain score will be attached to this document as appendices. This information is necessary to display if the intervention results in an increased comfort with the PNE procedure or increased satisfaction with the procedure. Number of voids and incontinence episodes before and after the PNE procedure is recorded to examine if a change in procedural effectiveness occurs with this intervention.

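### The primary t-test on VAS change is valid but usually less precise than a prespecified ANCOVA on a VAS taken before the patch

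*Combined protocol and SAP*

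**What the plan says.** The primary comparison is set in the Plan for Analysis of Results: "A two-sample t-test will be used to assess differences in the primary outcome of change in VAS score after procedure between groups". The same section adds "Throughout, a significance level of α =0.05 will be used, and all tests will be two-sided". Its only mention of modelling is "Multivariate linear/logistic regression models may be used to assess the impact of other variables onto primary or secondary outcomes". That sentence is permissive, names no baseline covariate and does not change the primary test.

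On measurement, Study design says "VAS pain scores prior to and immediately after procedure will be recorded", and the list of procedural variables under Research Materials, Records, and Privacy repeats "VAS pain score prior to and after the PNE procedure". The patch is also timed relative to the procedure: the trial is described as "comparing 4% lidocaine patch placed over the sacrum 30 minutes prior to the procedure to placebo patch". Neither place orders the prior VAS relative to the patch.

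The sample-size text in Study Design/Methodology uses "an assumed standard deviation for VAS score of 1.5 points", with a difference of 1.5 points and 17 women per group. It does not say whether that SD belongs to a single score or to the change, and it gives no pre/post correlation. On allocation it says "Participants will be randomized with a stratified block randomization scheme". The readable text names no stratification factor, and the analysis uses none.

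**The concern.** Subtracting the prior score from the post-procedure score fixes the baseline coefficient at 1. The coefficient that minimises variance is r × SD_post / SD_pre. With similar SDs this equals r, which is below 1, so subtraction adds noise from the prior score. It also carries any chance baseline imbalance into the estimate. That imbalance averages to zero over repeated randomisations but affects the one trial that is run. With 34 women, precision is scarce.

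Timing is the second part. The background text before Objectives says the patch can act within half an hour, and the patch goes on half an hour before the procedure. A prior VAS taken just before the procedure could therefore already reflect treatment. Part of the effect would then be subtracted out by the change score, or partly adjusted out by ANCOVA.

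**Working it through.** **Inputs from the documents:** difference 1.5, SD 1.5, 17 per arm, two-sided α = 0.05. **Assumed, because the documents do not give them:** r, the separate pre and post SDs, and which quantity the SD of 1.5 describes. Ranges are shown.

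**1. The plan's own figure.** SE = 1.5 × √(2/17) = 0.514, so the noncentrality is 1.5/0.514 = 2.92 on 32 df. Exact power is 80.7%, against 78.1% with 16 per arm. The 17 per group is reproduced when 1.5 is the SD of the analysed outcome.

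**2. Formulas.**
- Variance of change: SD_pre² + SD_post² − 2r·SD_pre·SD_post.
- ANCOVA residual variance: SD_post²(1 − r²).
- Difference between the two: (SD_pre − r·SD_post)², which is never negative.
- Price of ANCOVA: 31 df instead of 32, and a variance factor of 1 + 1/30 = 1.033 for estimating the slope.

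**3. SD 1.5 is for a single score and is equal at both times.** SD of change = 1.5√(2(1 − r)); residual SD = 1.5√(1 − r²).

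| r | SD change | Residual SD | Power, t-test | Power, ANCOVA | n per arm for 80% power (t-test / ANCOVA) |
|---|---|---|---|---|---|
| 0 | 2.121 | 1.500 | 51.6% | 79.3% | 33 / 18 |
| 0.3 | 1.775 | 1.431 | 66.6% | 83.0% | 23 / 16 |
| 0.5 | 1.500 | 1.299 | 80.7% | 89.4% | 17 / 14 |
| 0.7 | 1.162 | 1.071 | 95.4% | 97.3% | 11 / 10 |

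**4. SD 1.5 is for the change, with equal pre and post SDs.** Residual SD = 1.5√((1 + r)/2). The t-test has 80.7% power at every r. ANCOVA has 93.1, 89.4, 85.4 and 81.3% at r = 0.3, 0.5, 0.7 and 0.9.

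**5. Prior VAS varies less than post VAS (SD_post 1.5).**

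| SD_pre | r | Best slope | Power, t-test | Power, ANCOVA |
|---|---|---|---|---|
| 1.0 | 0.3 | 0.45 | 79.0% | 83.0% |
| 0.5 | 0.3 | 0.90 | 84.2% | 83.0% |
| 0.75 | 0.5 | 1.00 | 90.4% | 89.4% |

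When the best slope is near 1, subtraction is already close to optimal and ANCOVA pays about 1 point.

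**6. Chance imbalance.** A one-SD imbalance shifts the change estimate by (1 − r·SD_post/SD_pre) × SD_pre × √(2/17). With equal SDs of 1.5 the imbalance SD is 0.51, and the shift is 0.36, 0.26 and 0.15 points at r = 0.3, 0.5 and 0.7. With SD_pre 0.5 and r = 0.3 it is 0.02.

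**7. Validity.** In simulation with a pre-patch baseline, type I error was 4.7 to 5.1% for both methods, and both recovered the true difference of 1.5 (1.49 to 1.50).

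**8. Hypothetical post-patch baseline.** Suppose the patch has already lowered the prior VAS by an assumed 0.5 points (equal SDs of 1.5). The change score then estimates 1.5 − 0.5 = 1.00. ANCOVA estimates 1.5 − 0.5r, or 1.35, 1.25 and 1.15 at r = 0.3, 0.5 and 0.7. At r = 0.5, simulated power of the planned test falls from about 81% to about 47%.

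**The case against.** The planned test matches the stated hypothesis, which concerns change in VAS. If 1.5 is the SD of change, it meets the 80% target as it stands, so nothing is broken. This is conceded.

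The gain rests on quantities the documents do not supply. Chronic pain as the indication for the procedure is an exclusion, so prior scores may be low and tightly clustered, and ANCOVA may then gain nothing or lose about 1 point. This also stands. It limits the claim to usually more precise, and the documents do not show which case applies here. The widest contrast, 51.6% against 79.3%, needs r = 0 and the single-score reading of the SD. Much of it reflects that ambiguous sample-size input, so it should not set the priority.

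The timing gap may be an artefact, because the patient-flow figure is not shown and may give the order. The 0.5-point early effect is an illustration that no text supports. Both points are fair, but a covariate must precede treatment, so the order needs to be explicit in the text.

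The plan does allow regression on the primary outcome. That narrows the gap without closing it, because an optional model with unnamed covariates is not a prespecified primary analysis.

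**Conclusion.** The point holds as a recommended improvement, not as the correction of an error. In the cases computed with equal pre and post SDs, ANCOVA gains 16 points of power at r = 0.3, 9 at r = 0.5 and 2 at r = 0.7 if 1.5 is a single-score SD. If 1.5 is the SD of change, it gains 12, 9, 5 and under 1 point at r = 0.3, 0.5, 0.7 and 0.9. The loss in the low-spread cases is about 1 point. The comparison therefore favours ANCOVA unless prior VAS is known to vary little.

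These figures assume normal scores, 17 evaluable women per arm, a true difference of 1.5 and a prior VAS unaffected by the patch. Stratification terms were not modelled, because the factors are not named. The size of the gain is uncertain because r and the SDs are unknown. The validity of both methods with a pre-patch baseline is not in doubt.

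**What to change.** Replace the primary-analysis sentence with text such as:

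> The primary analysis is a linear model of post-procedure VAS on treatment group, with the VAS recorded before patch application as a covariate and the randomisation stratification factors included. The adjusted mean difference, its 95% confidence interval and the two-sided p-value are reported. A two-sample t-test on change in VAS is a sensitivity analysis.

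In Study design, state that the prior VAS is recorded before the patch is applied, and name the stratification factors. Make both changes before outcome data are seen.

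The cost is one sentence for the analysis and one for timing. The statistical price is one degree of freedom for baseline VAS, one for each stratification term, and about 3% variance inflation from estimating the slope. No extra patients or new instrument are needed. Women already attend ahead of the patch to give consent, so a pre-patch score needs no extra visit. If the prior VAS is currently taken with the patch on or after its removal, that assessment must be moved or a pre-patch one added; adjusting for the post-patch score is not a substitute.

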Page **3** of **17** Version Date: Lidocaine is frequently used for analgesia with PNE placement. This is often performed with injectable lidocaine, however, other forms can be considered to improve patient comfort and clinical success – namely through topical lidocaine patches. Up to 5% (35 mg) of lidocaine patches are absorbed topically, producing analgesia within 30 minutes with a half-life of 6 to 8 hours⁷. Transdermally absorbed lidocaine appears to have a very low rate of systemic absorption resulting in local analgesia and not anesthesia, a characteristic not shared with lidocaine infiltration. The exact mechanism of this differential effect is unknown, however, it is hypothesized that the lidocaine patch produces analgesia without blocking all the sensory and motor inputs in large, myelinated A- β sensory fibers ⁷. The value of this relatively rapid onset medication with analgesic effects and without the associated discomfort of infiltration can be increased comfort for patients. The ability to potentially detect adverse sensation more sensitively in the office may also make this method of analgesia more effective.

Objectives

Primary outcome will be:

• VAS pain scores measured on a 10 point scale before and after PNE procedure

Secondary outcomes will be:

- Patient Overall Satisfaction after PNE placement
- Volume of injectable lidocaine used
- Rate of successful PNE
- Progression to permanent SNS implantation.
- Amplitude of perineal stimulation

Page **4** of **17** Version Date: Our null hypothesis is that there will be no significant difference in change in VAS score between patients in the lidocaine patch group and the patients in the control group.

We hypothesize that patients in the lidocaine patch group will experience significantly less pain at the time of PNE as measured by change in VAS pain score when compared with the control group.

Study Design/Methodology

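### Fisher's exact test is valid but conservative for the two binary secondary outcomes at 17 per arm; Boschloo's exact test recovers some power at mid-range rates at no cost

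*Combined protocol and SAP*

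**What the plan says.** The Objectives section lists five secondary outcomes. Two are binary: "Rate of successful PNE" and "Progression to permanent SNS implantation". The section on Research Materials, Records, and Privacy defines a successful PNE by whether the wire was placed, and counts implantations at three months among patients with a successful PNE.

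The Plan for Analysis of Results gives the test: "Differences in secondary outcomes will be considered using the two-sample t-test for continuous variables and the Fisher exact test for categorical variables". It adds: "Throughout, a significance level of α =0.05 will be used, and all tests will be two-sided". Its fallback to transformations or non-parametric methods covers continuous data only. It reports counts and proportions by arm, but plans no interval for the difference between arms. Regression is optional: "Multivariate linear/logistic regression models may be used to assess the impact of other variables onto primary or secondary outcomes".

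Study Design/Methodology fixes the size: "Patient enrollment will conclude when 34 subjects, 17 of each group, have been enrolled in the study". The sample size rests on the VAS outcome alone. No expected rate and no power are given for either binary outcome.

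**The concern.** Fisher's test conditions on both margins of the 2×2 table. In small samples the attainable p-values are so few that the probability of a false positive can lie well below the nominal 5%. Part of the error rate that the plan allows itself then goes unused, and power goes with it.

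The plan says that symptom counts are collected to see whether procedural effectiveness changes, and its background suggests that the patch may make this form of analgesia more effective. The two binary outcomes bear on that question. In a trial of 34 patients, power that can be had for nothing is worth taking.

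**Working it through.** **Inputs.** 17 per arm and two-sided α = 0.05 come from the plan. All success rates below are assumptions, because the plan gives none.

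**The plan's own figure.** The plan claims "80% power to detect a difference between groups of the minimum clinically meaningful effect size of 1.5 points or greater", with "an assumed standard deviation for VAS score of 1.5 points". For the two-sample t-test the noncentrality is (1.5/1.5)·√(n/2). At n = 17 this is √8.5 = 2.92 on 32 degrees of freedom, giving power of 80.7%. At n = 16 power is 78.1%. So 17 per arm reproduces.

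**Method for the binary outcomes.** With a and b successes out of 17 there are 18 × 18 = 324 tables. For a rejection region R,

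- power(p₁, p₂) = Σ over (a, b) in R of Bin(a; 17, p₁) · Bin(b; 17, p₂);
- size = the maximum over p of power(p, p).

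Fisher's region is every table with a two-sided Fisher p ≤ 0.05. Boschloo's test uses the Fisher p as its statistic. Its p-value is the largest probability, over all common rates, of a Fisher p at or below the one observed. That probability cannot exceed the Fisher p itself, so Boschloo rejects whenever Fisher does.

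**Size at 17/17.**

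- Fisher: 144 rejecting tables, maximum size 2.44% (at a common rate of 50%). It is 1.94% at a common rate of 80% and 0.79% at 90%.
- Boschloo: 156 rejecting tables, maximum size 4.31%.

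**What is added.** 156 − 144 = 12 tables: 2 v 8, 3 v 9, 4 v 10, 7 v 13, 8 v 14 and 9 v 15 successes, and the same with the arms exchanged. For 9/17 v 15/17, Fisher gives p = 0.057 and Boschloo 0.027. For 8/17 v 14/17 the values are 0.071 and 0.035. None of the 12 tables has 16 or 17 successes in either arm.

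**Power at 17/17.**

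| Assumed rates | Fisher | Boschloo | Gain (points) |
|---|---|---|---|
| 48% v 83% (largest gain) | 44.6% | 56.4% | 11.9 |
| 50% v 85% | 45.7% | 57.2% | 11.5 |
| 50% v 80% | 31.9% | 43.1% | 11.2 |
| 40% v 80% | 56.1% | 66.3% | 10.2 |
| 30% v 60% | 31.3% | 38.7% | 7.4 |
| 50% v 70% | 13.6% | 20.1% | 6.5 |
| 70% v 95% | 34.7% | 35.8% | 1.1 |
| 80% v 95% | 11.6% | 11.7% | 0.1 |
| 90% v 95% | 1.0% | 1.0% | 0.0 |

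Gains are taken before rounding.

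**Sensitivity to the split.** At 17/16 Fisher's maximum size is 3.5% and Boschloo's 4.0%, and Boschloo's largest gain falls to 5.7 points. At 50% v 80% power goes from 34.8% to 38.7% (3.9 points) if the smaller arm has the 80% rate, and from 38.3% to 41.7% (3.3 points) if it has the 50% rate. At 16/16 Fisher's maximum size is 2.0% and the gain at 50% v 80% is 11.1 points. The gain is thus erratic in the arm sizes.

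**The case against.** The strongest case for leaving the plan alone is that Fisher's test is not wrong. It holds type I error at or below 5%, and conditional against unconditional testing is an old methodological choice. The outcomes are unpowered secondaries, and with no multiplicity adjustment stated, some conservatism may not hurt. Power stays poor under either test: at 50% v 80% even Boschloo reaches only 43.1%. All of this stands as a limit on importance. None of it names a practical loss from a test that rejects whenever Fisher does and keeps its size at or below 5%. If the plan wants stricter control across secondaries, it should set that openly and not leave it to the discreteness of a test.

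The arm sizes are a fair point too. Randomisation is stratified in random blocks of 4, 6 and 8, and implantation may be counted only among patients with a successful PNE. An exact 17/17 comparison is therefore a target and not assured, and the 2.4% figure belongs to that split alone.

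A reader might also infer that both outcomes lose some 11 or 12 points of power. The documents do not support that. They give no rates, and success is defined as wire placement. If that nearly always succeeds, the data fall where Boschloo adds no rejecting tables. Nor does 17/17 v 13/17 show a loss peculiar to Fisher: Fisher gives p = 0.103, but Boschloo gives 0.058, so both miss it.

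**Conclusion.** The point holds as a minor efficiency gain and not as an error in the plan. At an exact 17/17 split Fisher's test uses at most 2.4% of the allowed 5%. Boschloo's test uses up to 4.3% and is never less powerful.

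The 12-point figure is a ceiling, reached at mid-range rates and depending on the arm sizes. The likely beneficiary is progression to implantation, if its rates are mid-range. For wire placement with high success in both arms, changing the test does almost nothing, and an interval for the difference is the more useful addition.

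**What to change.** In the Plan for Analysis of Results, prespecify Boschloo's two-sided unconditional exact test in place of Fisher's for successful PNE and for progression to implantation. For each, report the risk difference with a 95% CI (Newcombe or Miettinen-Nurminen, one of them named in advance).

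State that the test governs significance and the interval describes the effect, because the two can disagree. For 17/17 v 13/17, for instance, Newcombe's interval runs from about 0.4 to 47 points and just excludes zero, while Boschloo's p is 0.058. The choice must be made before the data are seen. Switching after a Fisher p of 0.057 would not be acceptable.

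As an optional note, any logistic model for these outcomes could use Firth's penalised likelihood. If one arm has no failures, ordinary logistic regression has no finite odds ratio for treatment. With a common success rate p, the chance that at least one arm has none is 1 − (1 − p¹⁷)²: 31% at p = 90% and 66% at p = 95%.

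The cost is one or two sentences and standard R software, which the plan already uses. It needs no further patients or data, and the primary analysis does not change.

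### The primary t-test on change in VAS can be replaced by an unspecified method after the data are seen; fix one primary estimate in VAS points that a normality check cannot displace

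*Combined protocol and SAP*

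**What the plan says.** The section Plan for Analysis of Results names the primary test: "A two-sample t-test will be used to assess differences in the primary outcome of change in VAS score after procedure between groups". The same paragraph then sets a fallback for all continuous variables: "Transformations and/or non-parametric methods will be used if continuous data are found to substantially violate the assumption of approximate normality". Change in VAS is continuous and is not excepted. A further sentence makes regression optional: "Multivariate linear/logistic regression models may be used to assess the impact of other variables onto primary or secondary outcomes". The error rate is common to everything: "Throughout, a significance level of α =0.05 will be used, and all tests will be two-sided".

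The sample size text in Study Design/Methodology ties the trial to a difference in points. The size was chosen "so that we have 80% power to detect a difference between groups of the minimum clinically meaningful effect size of 1.5 points or greater", with "an assumed standard deviation for VAS score of 1.5 points". Recruitment is fixed: "Patient enrollment will conclude when 34 subjects, 17 of each group, have been enrolled in the study".

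On who sees what, Study Design/Methodology has the data analysed by study researchers, with de-identified data also going to the statistician. Research Materials, Records, and Privacy lists the randomization assignment among the database fields. The trial is described as double-blind, but nothing says that the analyst is blind to arm when normality is judged.

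**The concern.** The fallback leaves five things open for the only primary outcome: what counts as a substantial violation, which transformation, which non-parametric test, whether the check is made blind to arm, and which effect measure is reported afterwards. The and/or wording does not even settle how many replacement analyses there may be. The choice is made with outcome data in hand, possibly with arm visible, and a reader of the results could not tell how it was made.

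Two things are at stake. The first is the 5% level, which is assured for one fixed test but not for a choice among several. The second is the meaning of the result. The trial is powered on a mean difference of 1.5 VAS points, and neither a rank test nor a t-test on transformed values tests that quantity. Change in VAS can also be zero or negative, so a log or square-root transformation needs an added constant, which the plan does not give.

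**Working it through.** **1. The plan's own figure.** Inputs from Study Design/Methodology: difference 1.5, SD 1.5, two-sided α = 0.05, power 80%. Standardised difference d = 1.5/1.5 = 1.0. The two-sample t-test (noncentral t) needs n = 16.71, so 17 per arm and 34 in all. Power at 17 per arm is 80.7%. The stated size reproduces.

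**2. Type I error under different readings of the fallback.** The documents give no VAS distribution and no pre–post correlation, so three shapes were assumed: normal change scores, a bounded skewed VAS-like scale, and a lognormal post-procedure score. There were 20,000 null trials for each shape, 17 per arm. The Monte Carlo standard error is √(0.05 × 0.95/20,000) = 0.15 percentage points. The log test used an arbitrary shift.

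| Rule for the primary test | Normal | VAS-like | Lognormal |
|---|---|---|---|
| t-test always | 4.9% | 4.9% | 4.9% |
| Shapiro–Wilk p < 0.05 on residuals, then rank test | 5.0% | 5.4% | 5.5% |
| Shapiro–Wilk p < 0.05 on residuals, then log t-test | 4.9% | 5.5% | 5.6% |
| Smaller p of t and rank | 5.8% | 6.2% | 6.7% |
| Smallest p of t, rank and log | 6.4% | 6.7% | 7.1% |

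Further runs of a normality-triggered switch stayed between 4.9% and 5.8%. In one set, with four shapes, moving the Shapiro–Wilk cut-off from 0.05 to 0.01 left the error at 5.1–5.5%. The switch itself is therefore close to harmless. The larger excess needs selection on the p-value.

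**3. What each test addresses.** The t-test on change and ANCOVA both estimate a between-arm mean difference in VAS points. The rank test compares the ordering of values between arms. The log t-test compares means on a shifted log scale. Only the first two match the 1.5-point target.

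**4. What the proposed primary analysis does at 34 patients.** Read the SD of 1.5 as the SD of change, and let ρ be the pre–post correlation (assumed, equal variances). Then

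- variance of change = 2σ²(1 − ρ) = 2.25
- ANCOVA residual variance = σ²(1 − ρ²) = 2.25 × (1 + ρ)/2

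| ρ | Residual SD | Simulated power for 1.5 points | Simulated type I error |
|---|---|---|---|
| 0.2 | 1.5 × √0.60 = 1.16 | 95.0% | 5.1% |
| 0.5 | 1.5 × √0.75 = 1.30 | 89.6% | 5.1% |
| 0.7 | 1.5 × √0.85 = 1.38 | 85.5% | 4.9% |

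These are from 20,000 normal trials per cell and compare with 80.7% for the t-test on change. The plan states its SD for the VAS score. If 1.5 is the SD of a single score, the ANCOVA residual SD is 1.5 × √(1 − ρ²), or 1.47 at ρ = 0.2. The noncentral t with 31 degrees of freedom then gives about 82%. On either reading, 34 patients suffice over this range of ρ.

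**The case against.** The best defence is that this is ordinary fallback wording with a sound motive. The trigger is non-normality, not the p-value, and under that trigger the error rate barely moves, whatever cut-off is used. That stands.

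It can also be said that a rank test may serve the trial better. In simulations with assumed skewed or heavy-tailed data (SD 1.5, shift 1.5 points), Mann–Whitney power was 88% against 81% for the t-test (gamma), 97% against 83% (lognormal) and 95% against 85% (t with 3 degrees of freedom). That stands too, and it is the real price of the fix.

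A third defence is that group means and standard deviations will be summarised anyway, so a difference in points can be recovered. This is partly right. The difference could be calculated, but the primary p-value would belong to a different quantity.

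Finally, fixing the t-test already named would close the switch without ANCOVA. That is true. ANCOVA is preferred because it keeps the point scale and uses a baseline that is already collected, with the gain shown in the working.

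Three stronger readings are tempting, and the documents do not support them:

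- **That the plan inflates type I error.** It permits selection by p-value but does not plan it.
- **That regression is another replacement for the primary test.** The text offers it separately, to study other variables, and linear regression of change would keep the point scale.
- **That power falls below 80%.** A rank test loses power on near-normal data, but there the plan calls for the t-test.

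**Conclusion.** The concern holds as a gap in specification for the sole primary outcome. The primary test can be changed after the data are seen, with no criterion, named method, blinded check or effect measure. The possible effect on type I error is modest: about 5–6% if normality alone drives the switch, and about 6–7% if the test is picked by its p-value. The loss of the link to the 1.5-point target follows from what the tests estimate and needs no simulation. The error rates rest on assumed distributions, and the ANCOVA power figures on assumed correlations of 0.2–0.7 with normal data. The stated sample size is correct for the stated inputs and is not in question here.

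**What to change.** Amend Plan for Analysis of Results before the data are unblinded, to say that:

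- The primary analysis is the between-arm mean difference in VAS points, with 95% CI, from ANCOVA of post-procedure VAS on pre-procedure VAS and arm. It is two-sided at 0.05 and is not replaced whatever a normality check shows.
- Optionally, the p-value for this same estimate comes from a permutation test, if non-normality is a worry.
- The unadjusted t-test on change, one named rank test (for example Mann–Whitney) and any further regression with its covariates listed are sensitivity or secondary analyses that cannot replace the primary result.
- The transformation and non-parametric sentence applies to secondary continuous outcomes only.

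This costs one or two sentences. Both VAS scores are already collected, and the sample size stays at 34. The downside is small: the t-test now named becomes secondary, and a rank test cannot be made primary even if the data prove strongly skewed, when it could be the more powerful choice.
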